#### **Open label tDCS Sessions:**

Following the study end visit, individuals in the sham condition will be offered 10 open-label active tDCS sessions.

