# V. DESCRIPTION OF THE PROTOCOL

# The goal of this pilot study is to establish a structured protocol for safe remotely-supervised delivery of 40 consecutive tDCS sessions (active and control conditions) to be used in a randomized, controlled double-blind clinical studies in participants with MS.

*a)* Study Design: Participants will complete a total of 40 sessions across eight weeks: training at baseline with a study technician and then monitoring (through secure online video) by the study technician for the remaining thirty-nine sessions. We will use the most common montage of bilateral dorsolateral prefrontal cortex (DLFPC) placement, with the anodal electrode placed on the left side. This offers ease of reliable electrode placement and wide therapeutic applications. Dose will be up to the target of 2.5 mA with reduction to 2.0, 1.5, or 1.0 mA based on tolerability testing at baseline. At study end, participants in the sham condition will be offered 10 open label active sessions.

**b)** Study Equipment: For the remotely-supervised sessions, participants will be given the speciallydesigned tDCS device and headset, study laptop computer for secure video monitoring with study technician (must have internet access), a detailed reference manual, and a training video. The Soterix mini-CT is uniquely designed for remotely-supervised delivery and requires a one-time use code provided by the study technician to unlock the device for one stimulation session. The device will not operate without correct headset placement and has a single-button option to abort the session. The device will also automatically abort the session if optimal conditions are not maintained. It reports and records a completion code for each session.

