**c)** Randomization: Participants will be assigned to each condition in a 1:1:1 Stratified randomization procedure. Participants will be matched according to the degree of cognitive impairment (Symbol Digit Modalities test or SDMT score) and neurologic (motor) impairment (Expanded Disability Status Scale or EDSS score). Participants will be randomized to either the active tDCS condition paired with cognitive remediation or one of the two control conditions. The positive control condition will consist of cognitive remediation paired with sham tDCS and the negative control condition will consist of active tDCS with non-adaptive puzzle and board games using block randomization of permuted block sizes 3 and 6, based on our experience in cognitive remediation trials. SDMT performance will be categorized compared to published age-normative means (>0.99 SD, 1 to 2 SD and 2 to 3 SD below mean) and EDSS score will be categorized as mildly or moderately impaired (0 to 3.0 vs. 3.5 to 8.0).

d)*Outcome Measures:* Before and after each session, participants will complete brief measures to monitor for any stimulation-related events as well as mood and fatigue. In addition a pain scale will be administered during the session. Participants will also complete baseline and study-end inventories of mood and fatigue and complete a brief battery of cognitive tests including the Brief International Assessment of Cognition in MS or BICAMS, to help guide power estimates for the future trials. A summary of outcome measures can be found in Table 2.

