# VI. METHODS AND PROCEDURES

All remotely-supervised sessions will be completed while connected to a video session with the study technician. The protocol is designed to have a decision-tree series of checkpoints that must be met in order to proceed at each step (Figure 2). These checkpoints address compliance (attendance, ability to complete the procedures as instructed, following the study guidelines) and tolerability (at any time, if any predefined events are reported). Following state of the art in tDCS research, devices will be programmed in advance by the PI to provide either active or sham sessions following current standards for blinding. During a sham session, the device is programmed to ramp up to the desired intensity (target 2.5 mA) and ramp down for the initial 60 seconds, with no current delivery during the following 18 minutes of the session, and then current is ramped up and down for 60 seconds at the end of the session. These brief periods of stimulation serve to mimic the effects of a true stimulation session. Both participants and study coordinator (who administers study outcome measures) will be blinded, and will be asked to guess the assigned condition at study end.

The PI will not be blinded to study condition. The PI or an un-blinded study technician will preprogram devices according to randomization and then provide to the study coordinator for each participant. That is, the study coordinator and participant will be blinded to which condition programmed to the assigned device. All procedures will be the same for all three conditions. Adverse events will be addressed in either condition, and the study PI will always know the assigned condition for each participant.

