# **Remotely Monitored Study Sessions 2 to 40:**

These sessions will be completed from home with remote monitoring by the study technician. For participants in the sham condition who elect 10 additional sessions of the open-label, active tDCS, these same procedures will be repeated.

Participants will schedule times during which they are certain they can self-administer the tDCS while they are being remotely monitored by study staff. They will be observed using a secure internet-based video chat program that will be installed in the laptop they will use for the study. To start their session, the participant will connect to study staff via a secure internet-based video program.

They will put on the tDCS headgear while being monitored, and tell study staff if the device feedback indicates that the electrodes are acceptably placed. The participant will then receive the activation code from the tDCS device. If the study staff observes the participant making any errors that may cause the latter discomfort they can intervene with instructions for correction.

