#### Monitoring

We will utilize operating procedures for reviewing patient safety data and source data generated from this study. This will include weekly meetings between the PI. Co-investigators, and study coordinator. At these meetings, the entire research team will review the clinical ratings, assessments, clinical course, and medical records for each subject. Consideration of dropping any patient from the study for any reason will be discussed. If after the completion of the first 10 subjects the compliance is significantly less in one or more arm of the study relative to our previously observed compliance rates, the study will be put on hold and reviewed. Based on the extensive body of literature using tDCS across a range of conditions, and our initial participants studied to date (completed at Stony Brook Medicine, we have had >94% compliance in the active condition. Therefore, this discrepancy in compliance is not expected. We would define discrepancy in compliance as >50% difference in mean number of visits completed and/or 50% difference in number of "completers" in each condition (defined by completing at least 50% of n=5/10 sessions). If there is significantly poor compliance in the active session, we will be able to identify reasons including tolerability as well as symptom experiences. Tolerability is measured before, during and after each session and all participants will be monitored for all sessions. Safety is carefully addressed in our protocol with a series of stop criteria and clearly defined action items.

Specific attention will be given to data quality and timeliness, HIPAA-complaint, safe storage of data, and data backup of electronic source data. Attention will also be given to participant recruitment, accrual and retention, participant risk versus benefit, adverse events, and other factors that can affect study outcome, including scientific or therapeutic developments that may have an impact on the safety of the participants or the ethics of the study.

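### The open-label offer made only to sham participants is not kept from the blinded outcome coordinator, so active versus sham can be predicted above chance for later cognitive-training participants

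*Combined protocol and SAP*

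**What the plan says.** **The offer.** Section V(a), Study Design: "At study end, participants in the sham condition will be offered 10 open label active sessions". Section VI, Open label tDCS Sessions, ties it to the individual's own study end visit, after which "individuals in the sham condition will be offered 10 open-label active tDCS sessions". Neither place names who makes the offer.

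**The open-label sessions.** Section VI, Remotely Monitored Study Sessions 2 to 40: "For participants in the sham condition who elect 10 additional sessions of the open-label, active tDCS, these same procedures will be repeated". Under Study End Visit, the participant hands the equipment back at that visit.

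**Blinding.** Section VI, Methods and Procedures: "Both participants and study coordinator (who administers study outcome measures) will be blinded". The PI is un-blinded. The PI or an un-blinded technician programs each device and passes it to the coordinator, and the plan states that "the study coordinator and participant will be blinded to which condition programmed to the assigned device". Participants and coordinator each guess the condition at study end.

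**Meetings.** Section IX, Monitoring: "This will include weekly meetings between the PI. Co-investigators, and study coordinator". The whole team goes through each subject's ratings, test results, course and records.

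**Allocation.** Section V(c): 1:1:1, stratified by three SDMT categories and two EDSS categories, "using block randomization of permuted block sizes 3 and 6".

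**The concern.** An offer confined to one arm works as an unblinding notice for that arm. It comes at each participant's own study end, about eight weeks after starting, while others are still being treated and tested. The participant concerned has already been assessed, so the worry is about later participants: within a stratum the arms are kept in balance, so each known past assignment shifts the odds for the next one.

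The contrast at risk is active versus sham among those doing cognitive training. Section IX, Statistical Analyses, builds its main hypothesis on it (a gain at least one standard deviation larger with active tDCS), using change scores to study end. An assessor with an informed guess can, without intending to, vary encouragement, prompting or borderline scoring.

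There is also a consequence for Aim 1, which tests the sham procedure by who correctly identifies sham. If the coordinator's guesses are counted, correct guesses drawn from earlier open-label offers could be misread as a failure of the sham device.

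**Working it through.** The plan gives no figure for predictability of assignment, so there is none to reproduce.

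**Step 1: routes to the coordinator.** Three written procedures can expose the offer: programmed devices go through the coordinator; equipment returned at study end has to be issued again for open-label use; and the weekly review covers every subject with the coordinator present. No sentence diverts any of these for open-label participants.

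**Step 2: inputs.** From the plan: 85 randomised, 1:1:1, 3 × 2 = 6 strata (85/6 ≈ 14 each if equal), blocks of 3 and 6, eight weeks of treatment. Training participants: 85 × 2/3 ≈ 57. Assumed: block sizes equally likely, enrolment order and training task visible to the coordinator, study ends in order of enrolment, no dropout.

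**Step 3: hand calculation** for training participants, block known and complete, all earlier arms known.
- Block of 3 (one active, one sham): the first is a coin toss, the second is certain. Correct: (1/2 + 1)/2 = 75%; certain: 1/2 = 50%.
- Block of 6 (two and two): first 1/2; second 2/3; third 1/3 × 1 + 2/3 × 1/2 = 2/3; fourth 1. Correct: (0.5 + 0.667 + 0.667 + 1)/4 = 71%; certain: (1/3 + 1)/4 = 33%.

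Simulation with a single block size gives 74% and 48% for blocks of 3, and 69% and 29% for blocks of 6. These are slightly lower because the last block in a stratum is often incomplete.

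**Step 4: simulation with mixed blocks.** 400 trials per scenario. For each training participant, the probability of active versus sham is computed from earlier participants in the same stratum, over all possible block positions.

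| What the coordinator sees of earlier participants | Correct guess | Certain |
|---|---|---|
| No sham assignment disclosed | 50% | 0% |
| Every sham case, at the later participant's study end | 71% | 14% |
| Same, unequal strata | 71% | 14% |
| Same, past games-arm membership not visible | 70% | 8% |
| Acceptances only, 70% accept | 63% | 3% |
| Acceptances only, 50% accept | 59% | 2% |
| Every sham case, at the later participant's baseline, accrual 12–24 months | 56–62% | 4–8% |

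Acceptance rates and accrual times are assumptions; the plan gives neither. In the second row about half of training participants can be called with at least 75% confidence. A separate simulation with accrual spread over 52, 104 or 156 weeks gives 71% correct and 13–15% certain throughout.

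**Step 5: what drives it.** A guesser who ignores block sizes and names whichever training arm is behind in that stratum is correct 70.7% of the time (4,000 trials). A tally that ignores strata reaches 59%. The information comes from disclosure combined with balance within strata. Knowing the block sizes adds nothing to average accuracy, and with no disclosure accuracy is 50% even when blocks, strata and the games arm are known.

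**The case against.** The strongest reply is that disclosure is nowhere stated. The offer is written in the passive, home sessions are monitored by a technician or study staff rather than by the coordinator by name, an un-blinded PI and technician already exist, and the list of matters for the weekly meeting does not mention allocation or open-label status. A careful team could already be handling this correctly. That stands as far as it goes: exposure is the likely result of following the text, not something the text declares.

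A reader might infer more than the documents support:

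- *That the coordinator can work out assignments.* With mixed blocks the block boundaries are hidden, and even at the ceiling only 13–15% are certain. The deduction that one known sham in a block of 3 makes the other training participant active requires knowing that the block is of size 3 and where it starts.
- *That the double-blind claim fails.* Participants' blinding during treatment is untouched. The coordinator's blinding is weakened, not removed. Mood and fatigue inventories are completed by participants, and the Aim 1 completion count rests on device codes. Tests given by an examiner are the exposed part, although Table 2 does not state the mode of administration.
- *That printing the block sizes is the fault.* Step 5 shows that withholding them would leave average predictability unchanged.

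The end-of-study guess is a partial safeguard: it may detect a leak, but it does not prevent one and may itself be contaminated. The pilot status of Aim 2 lowers the stakes somewhat, but the declared purpose is a protocol for later double-blind trials, which would inherit the gap.

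**Conclusion.** The point holds as a gap in protecting the assessor's blind. The offer marks sham participants one at a time, and the written procedures lead it past the person who administers the outcome measures.

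Of about 57 training participants, chance gives about 28 correct guesses (0.50 × 57). The ceiling is about 40 (0.71 × 57), with 7 to 9 certain (13–15%). If only acceptances are seen, it is about 33 to 36 correct (59–63%), with 1 or 2 certain (2–3%). The ceiling assumes that every sham case is recognised and every stratum tracked. All figures rest on the assumptions in Step 2; the share that is certain depends on the mix of block sizes, whereas average accuracy hardly does.

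The size of any resulting bias in test scores cannot be derived from the documents. The leak is partial, but it falls on the main Aim 2 contrast and closing it is cheap, so the change should be made.

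**What to change.** Amend Section VI (Methods and Procedures; Remotely Monitored Study Sessions 2 to 40; Open label tDCS Sessions) and Section IX (Monitoring) to say that:

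1. The PI or the un-blinded technician makes the open-label offer, re-issues the device directly to the participant, and runs and records the open-label sessions. The coordinator takes no part.
2. Open-label participants are discussed in a part of the weekly meeting that the coordinator does not attend.
3. The coordinator has no REDCap access to open-label forms until the last participant's study-end battery is complete.

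Withholding the block sizes from the coordinator is not needed for this purpose.

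The offer itself, who receives it and when are unchanged. The cost is a few sentences, a change of access rights and a split agenda, all with existing staff. The one drawback is that scheduling open-label sessions falls on the un-blinded technician. With no disclosure, the calculation above returns 50% correct and 0% certain.

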#### VII. SUBJECT SELECTION

#### **Characteristics of the Research Population**

We will enroll a total of n=85 adults (ages 18 and over) with confirmed MS. Participation will be open to those with all subtypes and levels of disability who meet the eligibility criteria as below.

#### **Eligibility Criteria**

Enrolled participants must have a diagnosis of MS (any subtype) with stable disease status and expanded disability status scale (EDSS) scores of less than 6.5 or above with proxy. Individuals with a Symbol Digit Modalities Test or SDMT  score  $\geq$  3.0 SD below published norms will be excluded as will those with any health condition contraindicated with the use of a tDCS device (including history of seizures, abnormal EKG, skin disorders, head trauma or medical device in the head or neck). Baseline screening evaluation will include a neurological exam and medical clearance by the study physician and brief screening evaluations for ability to operate the study equipment.

Inclusion Criteria	Exclusion Criteria

 
Ages 18-79
 
Definite MS diagnosis, all subtypes [95]
 
MS-related changes in cognitive functioning*
 
A score of 6.5 or lesson the Expanded Disability Status Scale (EDSS) OR more than 6.5 with proxy
 
	
 
Visual, auditory and motor deficits that would prevent full ability to understand study instructions or operate the tDCS device or study laptop, as judged by treating neurologist or study staff
 
Relapse or steroid use in previous month
 

 
Has stable and continuous access to internet service at home compatible with the study laptop (Wi-Fi or ethernet cable)
 
Adequate internet capacity for remote monitoring, as tested by
 
	
 
History of mental retardation, pervasive developmental disorder or other neurological condition associated with cognitive impairment
 

 
http://www.speedtest.net/)
 
Adequate home facilities (enough space, access to quiet and distraction free area)
 
	
 
Primary psychiatric disorder that would influence ability to participate
 
History of seizures or seizure disorder
 


 
Able to commit to the two-week period of training sessions with baseline and follow-up visits.
 
Able to understand the informed consent process and provide consent to participate in the study
 
	
 
History of head trauma (e.g., head injury, brain surgery) in the past year or medical device implanted in the head (such as Deep Brain Stimulator) or in the neck (such as a Vagus Nerve Stimulator)
 
Any skin disorder/sensitive skin (e.g., eczema, severe rashes), blisters, open wounds, burn including sunburns, cuts or irritation, or other skin defects which compromise the integrity of the skin at or near stimulation locations (where electrodes are placed)
 
Treatment for a communicable skin disorder currently or over the past 12 months
 
History of uncontrolled or labile hypertension.
 
Other serious uncontrolled medical condition (e.g., cancer or acute myocardial infarction)
 
History of clinically significant abnormalities on electrocardiogram (EKG)
 
Alcohol or other substance use disorder
 
Learned English language after 12 years of age
 
Pregnant or breastfeeding
 
Symbol Digit Modalities Test ≥3.0 SD below published norms
 

---	---

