# IV. SPECIFIC AIMS

Specific Aim 1: To test the feasibility of a randomized, controlled remotely-supervised tDCS clinical trial protocol developed specifically for use in MS. Participants (n=85) will be randomly assigned to receive 40 x 20-minute sessions of either active (up to 2.5 mA) paired with cognitive remediation, to two separate control conditions. The first is an active tDCS condition paired with non-adaptive, traditional puzzle and board games and will act as this study's negative control. The second control will act as the study's positive control and will be sham tDCS paired with cognitive remediation. Each study session, regardless of study arm, will be followed by an additional 10 minute computerized training sessions post-stimulation. Each study arm will complete 40 sessions over eight weeks.

The *primary outcome* for feasibility will be the number of participants completing at least 80% or n=32of the targeted 40 sessions. Secondary outcomes will be comparison of tolerability and participant- reported side effects between the two treatment arms.

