# e)Analytic Plan:

Specific Aim 1 is to determine feasibility; to be measured by the number of participants successfully completed using the proposed protocol for training and monitored administration. As would be expected, there is a high rate of compliance for in-clinic tDCS administration and therefore remotely-supervised administration should be designed to be similarly compliant. Study success will be defined by 80% participants having completed 80% sessions, shown to be the target compliance for previous tDCS studies. We will also determine the effectiveness of our sham procedures to ensure blinding, as tested by comparing those who accurately identified the sham condition. We will assess whether the frequency or type of side effects differ between the active and control conditions and whether they occur at the same rate as reported from studies of in-clinic administration. Secondary outcomes will be tolerability, participant-reported adverse events, and comparisons of active and control conditions on these measures.

Specific Aim 2 will be to determine preliminary signals for efficacy, and to have pilot findings to determine necessary sample sizes for an adequately-powered clinical trial. For each participant, change scores will be calculated between baseline and study end scores on measures of fatigue and cognitive functioning. These difference scores will then be described and compared between groups (t-tests and ANOVA related analyses) to determine signals of efficacy for active tDCS paired with cognitive remediation vs. active tDCS paired with non-adaptive puzzle and board games vs. sham tDCS paired with cognitive remediation.

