# **Statistical Analyses**

Analyses will be completed with IBM SPSS v. 23. Means, medians, standard deviations (SD) will be compared between subgroups on the measures using conventional cut-off points for each of the symptoms will be compared.

Specific Aim 1 will be tested by comparing the number of participants in each condition meeting the study definition of compliance (having completed 80% sessions). We will also determine the effectiveness of our sham procedures to ensure blinding, as tested by comparing those who accurately identified the sham condition. We will assess whether the frequency or type of side effects differ between the three conditions and whether they occur at the same rate as reported from studies of inclinic administration.

Specific Aim 2 will be to determine preliminary signals for efficacy, and to have pilot findings to determine necessary sample sizes for an adequately-powered clinical trial. For each participant, change scores will be calculated between baseline and study end scores on measures of fatigue and cognitive functioning. These difference scores will then be described and compared between groups (t-tests and ANOVA related analyses) to determine signals of efficacy.

Cognitive performance will be evaluated for those who completed at least 18 sessions. We conservatively plan for comparison of 15 participants in each group, allowing for up to 33% dropout. While both cognitive remediation groups are expected to improve with cognitive training, we hypothesize that the active tDCS condition will gain one standard deviation (of the published normative mean) or more in score than the sham condition and that the group with active tDCS paired with non-adaptive puzzle and board games will neither improve nor decline.

Secondary outcomes will be used to compare the groups in change in performance on the additional measures listed in Table 2. These are the most commonly-used outcome measures in MS trials

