#### **Methods and Procedures**

Will mirror the exact methods detailed in section **VI**, with the exception that this study will be an open label feasibility study, with all participants receiving active, open-label tDCS. The exploratory aim to test the methods in a PD population will also run for a shorter duration. The treatment will occur over the course of 10 days rather than 40 to test initial feasibility of the methods in PD. Participants will attend the initial baseline visit in clinic, with the remaining 9 sessions occurring from home with remote supervision.

PD Specific Outcome Measures: Before and after each session, participants will complete brief measures to monitor for any stimulation-related events as well as mood and fatigue. In addition, a pain scale will be administered during the session. Participants will also complete baseline and study-end inventories of mood and fatigue and complete a brief battery of cognitive tests, to help guide power estimates for the future trials. A summary of outcome measures can be found in Table 3.

Test	Screening	Baseline	Daily Study Sessions (2- 10)	End of Study Session	Online/ Telephone Survey (Study end date + 1 month)
Medical Clearance	X				
Expanded Disability Status Scale	X			X	
Wide Range Achievement Test (WRAT-4)	X	X			
Symbol Digit Modalities Test (SDMT)	Х	Х		Х	
Beck Depression Inventory-Fast Screen		Х		X	
tDCS Aptitude Test		Х			
tDCS Tolerance Test (2.0 mA, will possibility to repeat at 1.5 mA)		Х			
Multiple Sclerosis Neuropsychological Questionnaire (MSNQ)		X		Х	Х
PROMIS Measure of Fatigue, Mood and Health-Related Quality of Life		X		X	X
Neuro-Quality of Life		Х		X	Х
Fatigue Impact Scale		X		X	X
Fatigue Severity Scale		Х		Х	Х
Pittsburgh Fatigability Scale		Х		X	

Table 3

Attention Network Test-	Х		Х	
Interaction				
Cogstate Brief Battery	Х		Х	
ERTSLab Processing Battery	Х	X	X	
Controlled Oral Word Association	Х		X	
Rey Auditory Verbal Learning Test	Х		X	X (delayed recall only)
Brief Visuospatial Memory Test- Revised	Х		X	
King Devick Test	Х		X	
Test of Everyday	Х		X	
Cognitive Ability				
Grip Strength	Х		X	
Grooved Pegboard	Х		Х	
Positive and Negative Affect Scale (PANAS)	Х	X	X	
Visual analog scale for fatigue (pre- and post- session)	X	X	X	
Visual analog scale for pain (pre-, early-, mid- and post-session)	Х	X	X	
Tolerability questionnaire - administered by study staff		X		
(pre- and post-session) Safety and tolerability questionnaire –self- report (pre- and post- session)		X		

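### The MS inclusion table asks for a two-week commitment, although every MS arm runs for eight weeks and 40 sessions

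*Combined protocol and SAP*

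**What the plan says.** All references are to the combined protocol and SAP.

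- **Eligibility.** The MS inclusion table (section VII, Eligibility Criteria) lists one criterion on time commitment: "Able to commit to the two-week period of training sessions with baseline and follow-up visits".
- **Regimen.** Specific Aim 1 (section IV) states: "Each study arm will complete 40 sessions over eight weeks". The Study Design paragraph (section V, item a) agrees: "Participants will complete a total of 40 sessions across eight weeks".
- **Primary feasibility outcome.** Section IV defines it as "the number of participants completing at least 80% or n=32of the targeted 40 sessions". The Analytic Plan (section V, item e) adds: "Study success will be defined by 80% participants having completed 80% sessions".
- **Cognitive evaluation.** Section IX, Statistical Analyses, states: "Cognitive performance will be evaluated for those who completed at least 18 sessions".
- **Parkinson's disease aim.** Section XI has a shorter schedule: "The treatment will occur over the course of 10 days rather than 40". Its own inclusion table carries the same two-week line.

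**The concern.** An eligibility criterion is what staff check and document for each candidate. This one describes a treatment period a quarter as long as the one MS participants are asked to complete. The mismatch touches the primary outcome directly, because Aim 1 counts participants who finish enough of the 40 sessions. A time-commitment criterion is the screening step that should protect that count. As written, it gives staff no listed ground for declining a candidate who can manage a short run of sessions but not eight weeks of them. A participant lost for that reason would count against the feasibility of remotely supervised stimulation, although the cause lay in the screening line.

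**Working it through.** No sample size, power or alpha figure depends on this point. The check is simple arithmetic and a comparison of sections.

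**Inputs**
- MS regimen: 40 sessions in 8 weeks (sections IV and V)
- Commitment asked of MS candidates: 2 weeks (section VII)
- Completion threshold: 80% of 40 sessions (section IV)
- Threshold for cognitive evaluation: 18 sessions (section IX)

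**Arithmetic**
1. The plan's own threshold reproduces: 0.80 × 40 = 32 sessions.
2. Average pace: 40 / 8 = 5 sessions per week.
3. Sessions covered by the stated commitment: 2 × 5 = 10, and 10 / 40 = 25% of the regimen.
4. Time needed for completion: 32 / 5 = 6.4 weeks. Two weeks falls 32 − 10 = 22 sessions short.
5. Time needed for cognitive evaluation: 18 / 5 = 3.6 weeks. Two weeks falls 18 − 10 = 8 sessions short.

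**Could two weeks refer to something else in the MS design?**
- *Initial training.* Section V places it at baseline, with the other 39 sessions monitored remotely. It is not a two-week period.
- *Interval between visits.* Under Study End Visit (section VI), the final visit falls within three days of the last session. On schedule, baseline and follow-up are therefore about eight weeks apart. Table 2 puts mid-study testing between sessions 20 and 21, which is 20 / 5 = 4 weeks in, already past two weeks.
- *Open-label extension.* Ten sessions would take two weeks at this pace, but section VI says that "individuals in the sham condition will be offered 10 open-label active tDCS sessions". That is an offer to one arm, made after the study end visit. It cannot be the training period that every candidate is screened for.

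**Where two weeks does fit**
- The earlier feasibility study described in section II gave 10 sessions in two weeks.
- The Parkinson's aim in section XI has 10 treatment days, so its identical line is right.
- The Monitoring text in section IX still defines a completer by 5 of 10 sessions. This suggests that wording from a 10-session design was carried over. That origin is an inference; the conflict does not depend on it.

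**The case against.** The strongest reply accepts the mismatch and disputes its consequence. Three parts of it stand, at least in part.

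- **Consent.** Process of Consent (section X) has staff go through the form and explain the procedures to each generally eligible candidate, and written consent precedes the first session. Every participant should therefore hear the real schedule. The consent form is not available here, so the duration it states cannot be checked. Consent informs the candidate, but it does not correct the criterion that staff document against.
- **The rest of the line.** The criterion also requires the follow-up visit, which falls at about week eight. Read whole, it does not plainly admit someone whose availability ends at week two. This is a partial answer, since being free for one visit is not a commitment to 40 sessions.
- **Size.** The session shortfalls all restate 10 against 40. They show a large gap on paper, not a shift in the outcome.

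A reader might go further and infer that the line puts the feasibility result at risk. If all 85 MS participants form the denominator, success needs 0.80 × 85 = 68 completers. That leaves room for 85 − 68 = 17 non-completers, and each person admitted on a two-week commitment would use one of those places. The documents do not support that reading. The denominator is an assumption, no count of such candidates is given, and nothing shows that staff would screen on two weeks while running a 40-session schedule.

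**Conclusion.** The point holds as a minor internal inconsistency: the MS commitment criterion is wrong as written. It names two weeks, or about 10 sessions, where the regimen is eight weeks and 40 sessions, the primary outcome needs 32 and the cognitive evaluation needs 18. The session counts assume an even pace of 5 per week, which is the protocol's average. The conflict between two and eight weeks needs no such assumption. The effect on enrolment or completion cannot be estimated, and the consent discussion and the follow-up visit both reduce it.

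One side note adds no weight. In the same Eligibility Criteria section, the paragraph and the table treat an EDSS of exactly 6.5 without a proxy differently: the table admits such a patient and the paragraph does not. A reader might take this as a second error with a known correction. The documents do not say which wording governs, and the aptitude test, the motor-deficit exclusion and medical clearance apply under either.

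**What to change.** In the MS inclusion table only, replace two-week with eight-week and state the 40 sessions, keeping the baseline and follow-up visits. Leave the Parkinson's table unchanged, because two weeks is right for its 10-day schedule. The new wording can apply to candidates screened after the change. It costs one line of text and alters no analysis, sample size or visit, since it matches the schedule every MS arm already follows.

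Separately, the sponsor should confirm which EDSS rule is intended at exactly 6.5 and use it in both places. That is the sponsor's decision, because adopting the table's wording would admit a patient at 6.5 without a proxy, whom the paragraph does not.
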